### **6.5. Concomitant Therapy**

Hormonal contraceptives that meet the requirements of this study are allowed to be used in participants who are WOCBP (see [Appendix 4](#)).

Medications that are taken after informed consent is obtained, but before the first dose of investigational product is received, will be documented as prior medications. The dosage and duration of all background RA medications will also be recorded on the eCRF for documentation of study eligibility. Medications taken after the first dose of investigational product has been administered will be documented as concomitant medications. Use of any allowed concomitant medications must follow local standard of care practices and regulations for the treated indication.

For participants who are on DMARD therapy (with the exception of methotrexate as specified in [Section 6.5.1.1](#)) and stable dose (at least 4 weeks) of leflunomide, anti-malarials and sulfasalazine the doses can be reduced or discontinued as per medical judgement. In the case of suspected COVID-19 infection, continuation of concomitant DMARD therapy should be carefully evaluated following local guidance and medical judgement, until full clinical assessment is completed. Initiation of additional DMARDs or an increase in the dose of current DMARD therapy during the study is prohibited. A combination of no more than 3 DMARDs is permitted during the study.

Participants are encouraged to bring their vaccinations up to date prior to initiating adalimumab; any live attenuated vaccine must have been administered at least 4 weeks prior to Day 1.

Participants previously treated for active TB infection, must have completed and documented a successful course of treatment in accordance with local guidelines. Participants detected with latent TB at Screening are eligible providing they have received at least 4 weeks of chemoprophylaxis and commit to completion of the full course of treatment, in accordance with local standard of care, before starting the study treatment. Participants whose chest radiography (or alternative chest imaging) and QuantiFERON®-TB Gold In-Tube Test results indicate no evidence of TB infection, but who are considered by the investigator to be at high risk to develop tuberculosis (eg, residing in high-risk areas or travel to high-risk areas), may be started on a course of TB prophylaxis or treatment in accordance with local guidelines at the discretion of the investigator. If TB prophylaxis treatment is started after the Screening visit, aminotransferases (ALT/AST) levels should be checked within at least 4 weeks prior to first investigational product in TP1 to confirm results fulfill entry criteria.

It is recommended that participants avoid changing prescription or non-prescription drugs, vitamins, and dietary supplements within 7 days or 5 half-lives (whichever is longer) prior to the first dose of investigational product and prior to study visits unless otherwise noted below, throughout the study.

Concomitant medications will be collected at each visit/contact from the time the consent form is signed to the final study visit/contact. All concomitant medication taken during the study (prescription, non-prescription drugs, and non-drug therapy as appropriate) must be recorded on the eCRF with daily dose, and start and stop dates of administration. If a participant discontinues early, concomitant medications must be followed at the EoT visit, the safety follow-up visit at least 28 calendar days after the last dose of investigational product, and any additional post-treatment phone contact and/or extended safety follow-up.

Concomitant medications prohibited in the study are summarized in [Appendix 10](#).

## **6.5.1. Stable Background Therapies**

### **6.5.1.1. Methotrexate**

Adalimumab must be administered concomitantly with a stable dose of MTX throughout the course of study treatment.

The administration of MTX, including dosage, laboratory testing, follow-up care (including contraception requirements), and contraindications should be performed according to local standards of care throughout the study.

At study entry, participants must have received oral or IM MTX for at least 12 weeks and have been on a stable dose of 10 to 25 mg per week for at least 4 weeks prior to first dose of investigational product. In geographic regions where 6 mg per week is a recommended initial dose by local guidance or standard of care, a stable dose of as low as 6 mg per week for at least 4 weeks prior to first dose of investigational product will be permitted.

Participants are required to continue their stable dose of MTX background therapy throughout the study. Dose reduction of MTX therapy during the study treatment is not recommended, with the exception of significant intolerance, and the dose reduction must be documented with the investigator's medical justification. Participants will not be discontinued from study treatment following a justified dose reduction of MTX, unless the MTX is adjusted below the minimal required dosage level of 7.5 mg/week (or a dose as low as 6 mg/week in geographic regions where permitted by local guidance or standard of care).

### **6.5.1.2. Folic/Folinic Acid Supplements**

Participants are required to receive a stable background dose of oral folic/foinic acid supplementation throughout the study. Participants must have received an adequate stable dose of oral folate (at least 1 mg/day on  $\geq 5$  days per week) or oral folinic acid ( $\geq 5$  mg once per week) for at least 21 days prior to first dose of investigational product and will continue on the regimen throughout the study treatment. In countries which do not have approved folic acid 1 mg or folinic acid 5 mg presentations, a regimen of folic acid of at least  $\geq 5$  mg weekly is acceptable.

### **6.5.1.3. Additional Background Therapies**

Participants may also continue additional concomitant therapies, including corticosteroids, a NSAID or Cyclooxygenase-2 (COX-2) inhibitor, and non-opioid and allowed opioid/narcotic analgesics (see [Section 6.5.2](#), [Section 6.5.3](#) and [Appendix 9](#)).

### 6.5.2. Pain or Other Arthritis Therapy

Participants may receive the following concomitant medications during the study under restricted conditions as specified below:

1. Participants may be taking one NSAID, including a COX-2 inhibitor. At the discretion of the investigator, the dosage may be adjusted to protect a participant's safety during the study.
2. Participants may additionally be receiving low dose aspirin for cardiovascular use ( $\leq 325$  mg per day).
3. Intra articular (IA) corticosteroids, oral and IM corticosteroids are allowed as rescue therapy, as described in [Section 6.5.3](#). Participants who enter the study with oral or IM corticosteroids must be on stable dosing regimen for at least 4 weeks prior to the first study treatment dose. At the discretion of the investigator, the corticosteroid dosage may be adjusted during the trial as per investigator's medical judgment. Tapering or discontinuation of the corticosteroid treatment should be performed as per local standard of care.
4. Participants receiving regular daily doses of only one of the allowed immediate-release opioids/narcotics (including tramadol) as listed in Table 2, and/or a regular a daily dose of up to 2 grams/day (or maximal local label daily dosage) of acetaminophen or 3 grams/day of paracetamol (eg, not using analgesic medication 'as needed') according to local guidance, must be on stable doses for at least 2 weeks prior to Day 1. Less frequent dosing or cessation of analgesic therapy should be performed as per investigator's medical judgment.
5. New or increased doses of following medications will be allowed as rescue therapy, as described in [Section 6.5.3](#).

**Table 2. Permitted Opioid/Narcotic Drugs**

Drug	Example Trade Names	Maximum Allowed Total Daily Dose
Tramadol	Ultram, Zydol, Zamadol, Ultracet, Tramal	300 mg
Codeine	Tylenol #2 and #3, Paveral	200 mg
Hydrocodone	Vicodin, Lortab	30 mg
Oxycodone	Roxicodone, Percocet, Tylox (not: OxyContin ® )	15 mg
Propoxyphene HCl or Propoxyphene napsylate	Darvon, Darvocet, Doloxene, Darvon-N, Darvocet-N 100	300 mg propoxyphene HCl 400 mg propoxyphene napsylate

### 6.5.3. Rescue Medicine

1. Analgesics: New or increased acetaminophen/paracetamol, current tramadol or other single opioid/narcotic drug (see Table 2), or another allowed opioid (see Table 3) are allowed as rescue medications according to the local label.

**Table 3. Additional Opioid Drugs for Rescue Therapy**

Drug	Example Trade Names	Maximum Allowed Total Daily Dose
Morphine	Short acting formulations (not: MS Contin ® )	30 mg
Hydromorphone	Dilaudid	7.5 mg
Meperidine	Demerol, Pethidine	300 mg

For participants who are receiving regular daily doses of one of the allowed opioids/narcotics:

- If the opioid/narcotic is tramadol, hydrocodone, or oxycodone, the dosage may be increased up to the maximum total daily dosage limits for rescue purposes. However, participants can NOT add a second opioid/ narcotic agent for rescue; therefore, any original opioid should be discontinued if a new opioid/narcotic is started for rescue.

For participants who are not on a regular daily opioid/narcotic therapy:

- Sustained release morphine formulations (eg, MS Contin®), sustained release oxycodone formulations (eg, OxyContin®), and propoxyphene HCL/napsylate are not allowed for rescue medication.
2. IA corticosteroids may not be administered within 4 weeks prior to Screening visit. However, IA injections of corticosteroids are allowed as rescue therapy in this study in accordance with the local label.

The following restrictions will apply when the rescue injections are performed:

- Rescue injections should be performed following the joint assessment after Screening visit.
- Investigators should follow local standard of care where participants should receive no more than one injection per month and no more than three injections per year.
- Arthrocentesis without injection of any IA medication is allowed. The joint having arthrocentesis will be considered as having its pre-injection status for the joint counts.

3. Non-pharmacologic treatment, including application of heat and cold, massage, physical therapy, splinting, or ultrasound is allowed.

## **6.6. Dose Modification**

No dose adjustment (dosage or dosing frequency) will be allowed in the study.

## **6.7. Intervention After the End of the Study**

No intervention will be provided to study participants after the end of the study.

## **7. DISCONTINUATION OF INVESTIGATIONAL PRODUCT AND PARTICIPANT DISCONTINUATION/WITHDRAWAL**

### **7.1. Discontinuation of Investigational product**

In rare instances, it may be necessary for a participant to permanently discontinue investigational product prior to completing the study. If investigational product is permanently discontinued, the participant will remain in the study to be evaluated for at least 28 calendar days after last dose of investigational product for monitoring of AEs/SAEs and concomitant medications.

Reasons for discontinuation from study treatment may include, but will not be limited to:

- AE potentially attributable to investigational product that in the opinion of the investigator endangers participant health or safety, including but not limited to severe hypersensitivity reactions, serious infections (see [Section 2.3](#) Benefit/Risk Assessment), active/latent tuberculosis, serious cardiac arrhythmias, or new or worsening congestive heart failure.
- Inadequate response to study treatment, in the judgment of the investigator (per local standard of care and/or guidelines).
- Participant noncompliance.
- Participant choice to withdraw from treatment (follow-up permitted by participant).
- Participant choice to withdraw from study participation (cessation of follow-up).
- Participant lost to follow-up.
- Participant pregnancy.

Note that discontinuation of investigational product does not represent withdrawal from the study.

See the [SoA](#) for data to be collected at the time of intervention discontinuation and follow-up and for any further evaluations that need to be completed.

### 7.1.1. Temporary Discontinuation

Temporary treatment discontinuation may be allowed in the case of an infectious AE or other potentially related AE occurring during the first 3 study Treatment Periods and the first 2 doses of TP4. Temporary treatment discontinuation should also be considered in the case of a known SARS-CoV2 exposure or suspected COVID-19 infection until full clinical assessment is completed.

Participants who experience a serious infectious AE (eg, life-threatening, requiring hospitalization, documented COVID-19 infection, etc.) or sepsis should be permanently discontinued from study treatment.

Delayed treatment due to other non-medical reasons (eg, participant is out of town and forgets to take their investigational product container) should be prevented as much as possible by discussing the participant's plans and educating him/her about the regular every other week dosing schedule. In TPs 1 – 3 and the first 2 doses in TP4, a participant who misses a dose should be instructed to take the missed dose as soon as he/she remembers, as long as the time elapsed following the intended dosing time is <7 days. He/she should take the next dose as scheduled. To be included in the PK analysis, it is critical for participants to not miss (see [Section 9.3](#)):

- The last 3 doses in TP4;
- The first dose of the study in TP1;
- No more than 1 missed dose per TP;
- No more than 2 missed doses allowed in TP1 through TP4;
- Participants can only miss or have an incomplete dose for either the first or second dose in TP4 (but not both).

A delayed treatment dose should be administered once the AE is resolved if the dose can be administered no later than 7 days before the next regularly scheduled dose of investigational product. Once 7 days passes from a regularly scheduled dose, the delayed dose in the previous 2 week dosing period will be considered missing (not delayed), and shall not be administered. For example, if the participant does not administer the investigational product on Monday (July 1), but is able to resume treatment on Sunday (July 8), the delayed July 1 dose may be administered on July 8. If the participant cannot resume treatment on July 8, the July 1 dose will not be administered (recorded as a missed dose), and the participant will receive the next regularly scheduled dose on Monday (July 15).

### 7.1.2. Permanent Discontinuation

Participants who experience a serious infectious AE (eg life-threatening, requiring hospitalization, documented COVID-19, etc.) or sepsis should be permanently discontinued from study treatment.

Permanent discontinuation would be considered for safety reasons or when either the participant or the investigator deemed necessary to discontinue investigational product.

## **7.2. Participant Discontinuation/Withdrawal From the Study**

A participant may withdraw from the study at any time at his/her own request.

At the time of discontinuing from the study, if possible, an early discontinuation visit should be conducted. See the [SoA](#) for assessments to be collected at the time of study discontinuation and follow-up and for any further evaluations that need to be completed.

The early discontinuation visit applies only to participants who are enrolled in the study or those who are randomized and then are prematurely withdrawn from the study. Participants should be questioned regarding their reason for withdrawal. The participant will be permanently discontinued both from the investigational product and from the study at that time.

If a participant withdraws from the study, he/she may request destruction of any remaining samples taken and not tested, and the investigator must document any such requests in the site study records and notify the sponsor accordingly.

If the participant withdraws from the study and also withdraws consent (see below) for disclosure of future information, no further evaluations should be performed and no additional data should be collected. The sponsor may retain and continue to use any data collected before such withdrawal of consent.

Lack of completion of all or any of the withdrawal/early termination procedures will not be viewed as protocol deviations so long as the participant's safety was preserved.

### **Withdrawal of Consent:**

Participants who request to discontinue receipt of study treatment will be discontinued from the study. The only exception to this is when a participant specifically withdraws consent for any further contact with him or her or persons previously authorized by the participant to provide this information. Participants should notify the investigator in writing of the decision to withdraw consent from future follow-up, whenever possible. The withdrawal of consent should be explained in detail in the medical records by the investigator, as to whether the withdrawal is only from further receipt of investigational product or also from study procedures and/or post treatment study follow-up, and entered on the appropriate CRF page. In the event that vital status (whether the participant is alive or dead) is being measured, publicly available information should be used to determine vital status only as appropriately directed in accordance with local law.

Please reference [Appendix 11](#) for details on participants discontinuing during the COVID-19 pandemic.

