  - The 2-week PK sampling period starts with Week 30 predose PK collection and ends with predose PK collection on Week 32.
- Safety Follow-Up Period begins after the last investigational product dosing on Week 32, and concludes at completion of the Week 36 assessments. All participants (including early discontinuations) will be followed for at least 28 calendar days from the date of their last dosed investigational product. Week 36 safety follow up may be conducted via phone.

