#### 4.4. End of Study Definition

A participant is considered to have completed the study if he/she has completed all treatment periods of the study, including the EoT visit (Week 32). The final safety follow-up is at Week 36, which may be done by phone. Early discontinuation from investigational product requires participants to return as soon as possible after the last dose of investigational product

for an EoT visit. A safety follow-up (may be done by phone) at least 28 calendar days after the last investigational product is also required.

The end of the study is defined when the last participant in the trial completes the date of last scheduled visit or contact as shown in the [SoA](#).

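### Protocol 7.2 removes from the study anyone who asks to stop treatment, while 7.1 keeps the same participant in for at least 28 days; the passages contradict each other and must be reconciled

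*Protocol*

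**What the plan says.** Protocol 7.2, in the paragraph on withdrawal of consent, gives the rule: "Participants who request to discontinue receipt of study treatment will be discontinued from the study". It continues: "The only exception to this is when a participant specifically withdraws consent for any further contact with him or her". The same paragraph then asks the investigator to document "whether the withdrawal is only from further receipt of investigational product or also from study procedures and/or post treatment study follow-up" and to enter this on the CRF.

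Protocol 7.1 states that after permanent discontinuation "the participant will remain in the study to be evaluated for at least 28 calendar days after last dose of investigational product", and adds: "Note that discontinuation of investigational product does not represent withdrawal from the study".

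Protocol 4.1 states: "All participants (including early discontinuations) will be followed for at least 28 calendar days from the date of their last dosed investigational product". Protocol 4.4 requires an end-of-treatment visit after early discontinuation and adds: "A safety follow-up (may be done by phone) at least 28 calendar days after the last investigational product is also required". SoA footnote 16 requires both an early-termination visit and a safety call at 28 days or later. Section 8.3.1 sets active AE and SAE collection for each participant to at least 28 days after the last administration. SoA footnote 18 does the same for concomitant medication after early discontinuation.

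The general text of 7.2 asks for an early discontinuation visit only where possible. It says the participant leaves both product and study at that point. It does not count missed withdrawal procedures as deviations, provided safety was preserved.

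**The concern.** A site holding this protocol finds two opposite instructions for a participant who says they no longer want the injections. Under one the participant leaves the study; under the other the participant stays for at least 28 days.

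At stake is the evenness of safety follow-up. Safety is a secondary objective. SAP 3.5.1 counts any adverse event after the first post-randomisation dose and gives no closing date. SAP 6.6.1.2 summarises events by arm and describes no adjustment for length of observation; the exposure summary in SAP 6.5.3 covers doses and treatment duration, not follow-up time. Because the trial is open-label, a request to stop may depend on the arm. If sites follow different sections, some of the time at risk after the last dose would go unobserved, and not necessarily equally in the two arms.

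**Working it through.** No figure in the plan is in dispute here, so the check sets the passages side by side.

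1. **Is it the same participant?** Yes. Section 7.1 lists the participant's own choice to leave treatment while allowing follow-up as a reason for discontinuing product, separately from the choice to leave the study. Section 7.1.2 also covers stopping on the participant's decision. Someone who declines further injections but accepts contact therefore falls under both 7.1 and the 7.2 rule.

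2. **Can both rules hold?** No. Section 7.1 has this participant remain in the study; 7.2 has them discontinued from it.

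3. **Does the exception in 7.2 rescue its rule?** Take the two possible rules in turn.
   - If the rule is removal, an exception for those who refuse contact would keep in only the people who cannot be contacted.
   - If the rule is remaining in the study, the exception makes sense, but that is not the rule in the sentence before it.

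   The two sentences cannot stand together. This does not settle which one the sponsor meant to keep.

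4. **Does the recording instruction fit?** It distinguishes stopping product only from stopping follow-up as well. If every request to stop ended participation, the distinction would have little purpose.

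5. **The early-termination visit.** It is required in 4.4 and SoA footnote 16, and only where possible in 7.2. Since 7.2 does not count missed procedures as deviations so long as safety was preserved, a site that stops early may leave no deviation on record.

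6. **Which data are exposed?**
   - Week 36 contact in the SoA: adverse events and concomitant medication, but no ADA/NAb and no drug-concentration sample. The 28-day follow-up itself yields no antibody data to lose.
   - EOT/ET visit in the SoA: one ADA/NAb sample and one concentration sample. The antibody risk is therefore at most one sample per participant, through the conflict in step 5. That sample can still matter, because SAP 6.2.2 classes a response as persistent or transient on the last sample.
   - Primary PK: the PK population in Protocol 9.3 and SAP 4 requires the Week 30 dose. Anyone who stopped before Week 30 is outside it under either rule. The residual case is a request made during the two-week sampling period.

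7. **How many participants?** The documents state no rate of requested stops, so no count follows. The sample-size section allows 420 − 314 = 106 non-evaluable participants, but that is a different quantity, as explained under the objection.

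**The case against.** The strongest reply is that other sections protect follow-up regardless of 7.2. Section 8.3.1 applies to each participant, and 4.1 names early discontinuations. Section 7.2 itself refers sites to the SoA, and it forbids further data collection only when a participant leaves the study and also withdraws consent for disclosure. The exception sentence and the recording instruction suggest a drafting slip. Part of this stands: no passage tells a site to stop collecting adverse events because treatment was declined, so divergence between sites is an inference. It does not remove the conflict. Section 7.2 is the section on leaving the study; it ends product and study together and lets missed procedures pass without a deviation.

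It is also fair that safety and immunogenicity are summarised descriptively, with no hypothesis test.

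Three stronger readings may tempt a reader, and the documents do not support them:

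- *Antibody data are lost broadly.* They are not: no antibody sample is scheduled after the EOT/ET visit, and 7.2 still asks for an early visit where possible.
- *The 25% non-evaluable allowance shows how many are affected.* It is a PK allowance. Under 9.3, non-evaluability also arises from missed or incomplete doses, missed PK samples, stopping methotrexate and other deviations, including in people who finish the study. The 420 are also counted from enrolment, before the Week 10 randomisation, so those who stop in the lead-in cannot bias a comparison of arms.
- *The CRF fails to separate stopping treatment from stopping follow-up.* Section 7.2 already requires the type of withdrawal to be entered on a CRF page. The CRF is not among the documents, so nothing can be called missing.

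**Conclusion.** The contradiction is certain and rests on the text alone. The rule in 7.2 is incompatible with 7.1 and with the follow-up requirements in 4.1, 4.4, 8.3.1 and the SoA; its exception does not fit its own rule; and the status of the early-termination visit differs between sections.

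The consequence is limited. The main exposure is up to 28 days of AE/SAE and concomitant-medication follow-up after the last dose, for participants who ask to stop. An effect on the arm comparison would need two things the documents do not establish: that sites apply the sections differently, and that requests to stop differ by arm. The matter should be corrected because an operative instruction cannot be followed as written, not because a given amount of data has been shown to be lost.

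**What to change.** Reconcile both sentences of the withdrawal-of-consent paragraph in 7.2, and the wording there that makes the early discontinuation visit conditional, with 7.1, 4.1, 4.4, 8.3.1 and SoA footnote 16. One rule should then state what happens after a request to stop treatment, and one status should apply to the early-termination visit. Which rule to keep is for the sponsor to decide. Issue a site clarification at the same time.

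The cost is two sentences and one phrase in a protocol amendment, plus a letter to sites. No visit or sample is added to the SoA.

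If participant follow-up is already complete, a descriptive table of follow-up time after the last dose, by arm and reason for stopping, would show whether the conflict had any effect.
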